#### **Objective 4: Assess participant experience and optimize outcome measures across sites.**

Well-developed content themes with data saturation emerging from feedback interviews will provide information on acceptability, impact of assessments, protocol and intervention fidelity, and equivalence of these markers across sites. Benchmark sensitivity and responsiveness values will determine the most sensitive and responsive measures relative to all study outcomes, versus a significance testing approach in which standardized/conventional threshold values are used to make decisions regarding significance. Sensitivity and responsiveness information will determine which outcomes are most impacted by MBRT for retention in a future full-scale multi-site efficacy trial. Benchmarks for equivalence across sites will be evidenced by: a) qualitative themes that suggest experiential continuity across sites, and b) equivalence in outcome measure response distributions, reliability estimates, and intraclass correlations.

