### **9.2.1 Treatment Assignment Procedures**

Randomization will be stratified first by study site, and then within study site by gender. We will employ a permuted-block randomization procedure, stratifying by gender, to assign participants to study arms. We will employ this randomization procedure to: 1) be able to optimize the study procedures we plan to use in a future fully-powered efficacy RCT, 2) obtain parameter estimates that reflect the causal impact of MBRT on outcomes, 3) assess measure sensitivity and responsiveness in a way that reflects the causal impact of MBRT on participants, and 4) ensure balance within strata and across study arms.

Using procedures piloted in our R21 (R21AT008854), following baseline assessment, study staff not involved in data collection will randomly assign participants to condition using SPSS and REDCap. The study statistician will create an allocation table using SPSS, and upload it to REDCap, which will be used to implement the randomization procedure at each site. All trial randomization codes will be stored within REDCap, which is a secure (HIPAA-compliant) internet-based survey and data management software system housed on a secure server at Oregon Health and Science University.

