## **9.6 Data Analyses**

### Quantitative:

Following best practice guidelines including CONSORT feasibility guidelines and past research, we will measure sensitivity (using a relative efficiency approach) and

responsiveness to change (examining within-group change over time). Relative efficiency analyses will be used to establish that our outcome measures are sensitive to differences between our treatment arm of focus (MBRT) and our other two arms - an active control arm (SME) and a no-treatment control arm (NIC). Therefore, sensitivity analyses will focus on assessing the degree to which outcomes are sensitive to study arms and not whether change is significant. Sensitivity to differences for MBRT compared to SME and NIC will be assessed by examining the relative efficiency of each outcome variable for MBRT versus SME and NIC separately. We will calculate the relative efficiency for MBRT versus SME by conducting one-way, between-subjects Analysis of Covariance (ANCOVA) analyses with MBRT versus SME as the independent variable and each outcome variable at post-training as the dependent variable; we will include study site and gender as covariates. We will also conduct ANOVAs using the same independent and dependent variables to ensure that all inferential tests are conducted and identify any potential Type II Errors among the ANCOVAs. We will then divide the *F*-statistic for each behavioral (BlueTeam/departmental use of force; individual indicators of use of force as well as a composite score of use of force using the individual indicators), physiological (C-RP, IL-6, IL-10, TNF- $\alpha$ ), and self-report (aggression, alcohol misuse, depression, suicidal ideation, trauma symptoms, burnout, and psychological resilience) outcome by the largest *F*-statistic among these analyses, such that the larger the number, the more sensitive that outcome is to the impact of MBRT relative to the active control group.

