To calculate the relative efficiency of MBRT versus NIC, we will conduct one-way, between-subject ANCOVAs with MBRT vs. NIC as the independent variable, each outcome variable at post-training as the dependent variable, and gender and study site as covariates. Again, we will also conduct ANOVAs using the same independent and dependent variables to ensure all inferential tests are conducted and identify any potential Type II Errors among the ANCOVAs. We will then divide the *F*-statistic for each behavioral, physiological, and self-report outcome by the largest *F*-statistic among these analyses; again, the larger the number, the more sensitive the outcome is to MBRT relative to the no-treatment control group. These sensitivity analyses will allow assessment of which behavioral, physiological, and self-report outcomes are most sensitive to MBRT.

Responsiveness to change across time will be assessed in the MBRT arm for behavioral, physiological, and self-report outcomes by: 1) calculating and comparing standardized mean responses (SMR) for outcomes by subtracting the baseline mean response for each outcome from the post-intervention mean response for that outcome, and dividing by the standard deviation of change for that outcome; 2) calculating and comparing partial correlation coefficients (adjusting for study site and gender) between a global impression of change measure that captures the subjective experience of changes in stress, job performance, and resilience at post-intervention and residualized change scores (baseline to post-intervention) for each self-report outcome. For both SMR values and correlation coefficients, the higher the absolute value, the more responsive the outcome is to change across time in the MBRT arm. We will conduct additional correlation analyses using the same variables without adjusting for study site and gender to identify any potential Type II Errors among the partial correlations.

In addition, we will examine data for any indications of systematic site differences. Using baseline data (where sample size will be greatest) and pooling arms, since no treatment differences are expected at baseline, distributions of standardized responses on outcome measures will be summarized, graphed, and compared across sites. Key parameters, reliability

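### The standardized mean response is an uncontrolled pre-post change in the MBRT arm, so it cannot carry the causal reading given to it in section 9.2.1 and Objective 4

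*Combined protocol and SAP*

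**What the plan says.** Section 9.6 (Data Analyses, Quantitative) uses two kinds of evidence to judge outcome measures. Sensitivity is a between-arm comparison: F-statistics for MBRT against SME and MBRT against NIC on the post-training score, with site and gender as covariates. Responsiveness is a single-arm assessment: "Responsiveness to change across time will be assessed in the MBRT arm for behavioral, physiological, and self-report outcomes".

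Responsiveness has two metrics. The SMR is obtained by "subtracting the baseline mean response for each outcome from the post-intervention mean response for that outcome, and dividing by the standard deviation of change". The second is a partial correlation between a global impression of change and "residualized change scores (baseline to post-intervention) for each self-report outcome". Both are ranked by size regardless of sign: "the higher the absolute value, the more responsive the outcome is to change across time in the MBRT arm".

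Two other places say what responsiveness is for. Section 9.2.1 lists, among the reasons for randomizing, the wish to "assess measure sensitivity and responsiveness in a way that reflects the causal impact of MBRT on participants". Objective 4 in section 1.1 says: "Sensitivity and responsiveness information will determine which outcomes are most impacted by MBRT for retention in a future full-scale multi-site efficacy trial".

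**The concern.** Randomization supports a causal reading only when randomized arms are compared. The SMR has no comparator term, so it adds together the effect of MBRT and whatever would have happened to these officers anyway. Shared change is plausible here: section 3 says the second cohort's baseline was delayed by COVID-19 restrictions, and the stress, mood, burnout and alcohol measures are repeated at each visit. Because absolute values are ranked, a shared trend in either direction can raise an outcome's rank. A trend opposite to a real effect can hide that effect.

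The stake is the choice of outcomes for the next trial. An outcome that moved in every arm could be carried forward as one that MBRT changes, while a truly affected outcome ranks lower. The plan reports no change statistic in SME or NIC beside the SMR, so a reader could not tell the two cases apart from the responsiveness results.

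**Working it through.** **Inputs from the documents.** N = 104, ratio 2:1.5:1, arms of 47, 35 and 22 (section 3); 20% attrition predicted (section 9.2); NIC completes the same assessments as the active arms (section 5.1). No power, effect size, SD, trend or SMR value is stated.

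**Arm sizes.** 104 × 2/4.5 = 46.2; 104 × 1.5/4.5 = 34.7; 104 × 1/4.5 = 23.1. These agree with 47, 35 and 22 to within about one participant. Assuming that the 20% attrition applies equally to each arm by the post-intervention visit: 47 × 0.8 = 37.6, 35 × 0.8 = 28 and 22 × 0.8 = 17.6, so about 38, 28 and 18 completers.

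**What the SMR estimates.** With a shared trend t and an MBRT effect d in baseline-SD units, equal variances and baseline-to-post correlation ρ, the expected value is about (t + d) / √(2(1 − ρ)). For d = 0:

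| Shared trend t | ρ = 0.5 | ρ = 0.7 | ρ = 0.8 |
|---|---|---|---|
| 0.1 | 0.10 | 0.13 | 0.16 |
| 0.2 | 0.20 | 0.26 | 0.32 |
| 0.3 | 0.30 | 0.39 | 0.47 |

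The MBRT-minus-control difference in mean change, divided by the pooled SD of change, has expectation 0 in every cell.

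**Precision, in SD-of-change units (approximate).**
- SMR: 1/√37.6 = 0.16; 95% half-width 1.96 × 0.163 = 0.32.
- MBRT minus NIC: √(1/37.6 + 1/17.6) = 0.29; half-width 0.57.
- MBRT minus SME: √(1/37.6 + 1/28) = 0.25; half-width 0.49.

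**Effect on ranking.** Simulation with at least 20,000 replicates per scenario, normal change scores, 38 MBRT and 18 NIC completers, correlation 0.3 between the two outcomes, and the plan's absolute-value rule. One outcome has a true MBRT effect and no drift; the other has shared drift and no MBRT effect. Drift, effect and correlation are assumptions. Entries are the share of trials in which the unaffected outcome ranks first.

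| Drift | Effect | MBRT-only SMR | MBRT minus NIC |
|---|---|---|---|
| 0.4 | 0.2 | 84% | 43% |
| 0.3 | 0.3 | 50% | 35% |
| 0.2 | 0.3 | 32% | 35% |
| 0 | 0.3 | 17% | 35% |

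Against SME (28 completers) the controlled figures in the first two rows are just over 40% and about 31%. The SMR error rate climbs with drift. The controlled rate does not depend on drift, but it starts higher because of its larger standard error.

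**Which metric is affected.** In a simulation of the second metric, without covariates, adding a uniform trend of 0.4 SD left the mean correlation at 0.327. A constant shift cannot change a correlation.

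**Regression to the mean.** Section 4.2 excludes severe scorers on four screening measures and sets no minimum severity. If the top 2% to 10% were removed on the outcome itself, the baseline mean would fall by 0.049 to 0.195 SD. Multiplying by (1 − ρ) with ρ from 0.5 to 0.7 gives an expected drift from 0.049 × 0.3 = 0.015 to 0.195 × 0.5 = 0.10 SD, toward higher scores.

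**The case against.** The strongest defence is that a within-arm SMR is a standard psychometric quantity and that section 9.6 labels it correctly, as change over time in the MBRT arm. That stands. The conflict lies with the wording of section 9.2.1 and Objective 4, and rewording those would by itself remove the contradiction.

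A second defence is that relative efficiency is already a controlled comparison in which a shared trend cancels, so outcome selection does not rest on the SMR alone. That also stands, but it does not repair the SMR. Relative efficiency compares post-training scores with no baseline score listed as a covariate, responsiveness is a separate input to the selection, and section 9.6 plans no comparison of change between arms.

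A third is that subtracting a control arm of about 18 costs precision. This is correct, and the last two rows of the ranking table show it.

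A reader might go further and infer that the whole responsiveness assessment is biased by time trends, that regression to the mean drives the problem, or that a controlled ranking is simply better. The documents support none of these. The global-impression correlation is not moved by a uniform trend. The stated exclusions imply only a small drift toward worsening; officers volunteering when stressed could push the other way, but no figure is given. The controlled ranking does better only once drift is appreciable. Nor is this an inflated efficacy claim: section 9.1 proposes no efficacy hypotheses.

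**Conclusion.** The plan is wrong as written in one respect: it gives a causal reading to an MBRT-only SMR that has no comparator. The point is confined to the SMR and to the wording in section 9.2.1 and Objective 4. Its size cannot be fixed from the documents. Over the assumed scenarios the SMR puts the unaffected outcome first in 17% to 84% of trials, against 35% to 43% for the MBRT-minus-NIC difference. At an effect of 0.3 SD of change the two break even at a shared drift slightly above 0.2. The harm is to the choice of outcomes for the next trial. The plan should be corrected, but the SMR need not be abandoned.

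**What to change.** 1. Keep the MBRT SMR as a descriptive measure and compute the same statistic in SME and NIC.
2. Report beside it the MBRT-minus-NIC and MBRT-minus-SME differences in mean change, divided by the pooled SD of change, with 95% confidence intervals.
3. Base any statement that an outcome is impacted by MBRT on the controlled contrasts.
4. Reword section 9.2.1 and Objective 4 so that the MBRT-only SMR is described as within-arm change and not as causal impact.

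The cost is SAP wording and one table; no new data are needed. The downside is noise: standard errors of about 0.29 and 0.25 against 0.16. The controlled differences should therefore accompany the SMR and not silently replace it. If the team chooses to rank on them, the SAP should say so and acknowledge the trade of bias for variance.

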# 6. STUDY PROCEDURES

## 6.1 Schedule of Evaluations

Assessmen	Phone Screen	Baseline, Enrollment, Randomizat ion: Visit 1	Post-interventi on: Visit 2	3 Month Follow-Up: Visit 3	6 Month Follow-Up: Visit 4
Verbal Consent	X				
Inclusion/Exclusion Criteria	X				
Informed Consent	X				
Alcohol Misuse	X	X	X	X	X
Depression	X	X	X	X	X
Suicidal Ideation	X	X	X	X	X
Trauma Symptoms	X	X	X	X	X
Medication Use		X	X	X	X

Assessment	Phone Screen	Baseline, Enrollment, Randomization: Visit 1	Post-intervention: Visit 2	3 Month Follow-Up: Visit 3	6 Month Follow-Up: Visit 4
Current Psychological Treatment		X	X	X	X
Tobacco Use		X	X	X	X
Adverse Childhood Experiences		X			
C-reactive protein		X	X	X	
IL-6		X	X	X	
IL-10		X	X	X	
TNF- $\alpha$		X	X	X	
Aggression		X	X	X	X
Psychological Resilience		X	X	X	X
Sleep Disturbance		X	X	X	X
Mindfulness		X	X	X	X
Self-Compassion		X	X	X	X
Burnout		X	X	X	X
Sustained Attention to Response Task		X	X	X	X
Interoceptive Awareness		X	X	X	X
Perceived Stress		X	X	X	X
Treatment Expectancy/Credibility (MBRT and SME)		X			
Global Impression of Change (MBRT and SME)			X		
Acceptability (procedures)			X		
Acceptability (MBRT and SME)			X		
Compliance (MBRT and SME)			X		

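### The anchor-based responsiveness ranking in section 9.6 compares outcomes from different domains against one change measure about stress, job performance and resilience, so it mixes content match with responsiveness

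*Combined protocol and SAP*

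**What the plan says.** Section 9.6 (Quantitative) defines two indices of responsiveness, both computed in the MBRT arm.

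- The first is "calculating and comparing standardized mean responses (SMR) for outcomes": mean change from baseline to post-intervention divided by the standard deviation of change.
- The second is a partial correlation, adjusted for site and gender, between "a global impression of change measure that captures the subjective experience of changes in stress, job performance, and resilience" and "residualized change scores (baseline to post-intervention) for each self-report outcome".

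One reading rule covers both: "For both SMR values and correlation coefficients, the higher the absolute value, the more responsive the outcome is to change across time".

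The same section lists the outcomes for the relative-efficiency comparison. The self-report part reads "self-report (aggression, alcohol misuse, depression, suicidal ideation, trauma symptoms, burnout, and psychological resilience". Of these seven, only resilience is named in the description of the anchor.

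The schedule in section 6.1 has one line for the anchor, "Global Impression of Change (MBRT and SME"), at the post-intervention visit. Neither that schedule nor the visit list in section 6.2.4 contains a change rating specific to alcohol, suicidal ideation, trauma, aggression or depression. Section 9.6 does not limit the comparison to outcomes whose content matches the anchor.

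Objective 4 in section 1.1 gives the use: "Sensitivity and responsiveness information will determine which outcomes are most impacted by MBRT for retention in a future full-scale multi-site efficacy trial".

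**The concern.** A correlation with a change anchor reflects two things: how well the scale tracks change in its own domain, and how closely that domain coincides with what the anchor asks about. When all scales measure the same construct, the second is roughly constant, and comparing correlations is a fair comparison of responsiveness. When the scales measure different constructs, it is not. Take an officer who drinks less but feels no different about stress, work or resilience. That officer lowers the alcohol correlation even if the alcohol scale recorded the change perfectly, and the rule in section 9.6 would read the result as poor responsiveness.

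Choosing measures for the efficacy trial is a main purpose of this study. Aggression is in its title, and alcohol misuse, trauma and suicide are in its rationale (section 2.1). An index that favours scales resembling the anchor pulls that choice in a direction nobody intended. Section 9.6 also gives no rule for reconciling this index with the others when they disagree.

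**Working it through.** The documents state no expected correlation, reliability or effect size for this analysis, so there is no figure of the plan's to reproduce. What follows is an illustration on stated assumptions.

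**Inputs from the documents.** The MBRT arm has 47 officers (sections 3 and 4.3) and predicted attrition is 20% (section 9.2): 47 × 0.80 = 37.6, taken as 38.

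**Assumptions.** Two outcomes change equally and have equal reliability, 0.75. Their latent changes correlate 0.3 with each other. They differ only in ρ, the correlation of latent change with the anchor, which is treated as free of error. Site and gender adjustment is left out.

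**Expected correlation.** Observed r ≈ ρ × √reliability, with √0.75 = 0.866. For example, 0.6 × 0.866 = 0.52 and 0.2 × 0.866 = 0.17.

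**How often the better-matched outcome has the larger |r|** (40,000 simulated trials, n = 38):

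| ρ, better matched v other | Expected r | Ranks higher |
|---|---|---|
| 0.6 v 0.2 | 0.52 v 0.17 | 97% |
| 0.6 v 0.3 | 0.52 v 0.26 | 92% |
| 0.5 v 0.3 | 0.43 v 0.26 | 82% |
| 0.5 v 0.4 | 0.43 v 0.35 | about 68% |
| 0.5 v 0.45 | 0.43 v 0.39 | 60% |

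With equal ρ the figure is 50%. If the anchor itself has reliability 0.7, the 0.5 v 0.3 row falls from 82% to 77%.

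**Are the other indices affected?** A second simulation (20,000 runs, n = 38) gave both outcomes a true SMR of 0.5 and reliability 0.8, and gave the anchor reliability 0.7. Here the anchor measures outcome A's domain exactly, which is an extreme case. True change in domain B correlates 1, 0.8, 0.6, 0.4, 0.2 or 0 with change in domain A.

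- On |r|, B ranks lower in 50%, 94%, 99%, 99.9%, 100% and 100% of runs.
- On the SMR, B ranks lower in about 50% of runs at every value.

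Relative efficiency is each outcome's F divided by the largest F. No anchor enters it, so it cannot be affected.

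**Precision.** With three covariate terms (two for site, one for gender), the standard error of Fisher's z is 1/√(38 − 3 − 3) = 0.177. A partial r of 0.30 then has a 95% interval of −0.04 to 0.58. Ranks on r would be unstable even without the content problem.

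**The case against.** The best defence is that the anchor has a limited role and may be less mismatched than it looks. Several parts of it stand.

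- **Other indices.** The SMR ranks the same outcomes without an anchor, and so do two relative-efficiency comparisons (MBRT v SME and MBRT v NIC). A reader might infer that the anchor decides the whole ranking, or that a low correlation would remove a measure from the future trial. The documents do not support that: Objective 4 rests on sensitivity and responsiveness information together, and nothing says that r alone excludes a measure.
- **Overlap of domains.** Section 2.1 itself links officer stress to aggression, depression and suicide, PTSD, burnout and alcohol misuse, and section 2.2 has mindfulness training act through stress appraisal. Perceived change in stress could therefore track several of these outcomes. The anchor's items are not given, so the degree of match is a judgement.
- **Floor effects.** Section 4.2 excludes officers in the severe range for depression, suicidal ideation, alcohol use or PTSD. Those scales may have little room to improve, so a low r could reflect truly low responsiveness in this sample. A reader might infer that any low rank on these outcomes is due to content alone. That does not follow.
- **Arms used.** Because the anchor is also collected in SME, a reader might infer that the correlation should pool both arms. The plan defines responsiveness as change in the MBRT arm (sections 9.1 and 9.6), and pooling would not touch the content mismatch.

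The interviews do not repair the gap. The sample outcome questions in section 9.6 cover resilience, coping with stress and day-to-day work, which is close to the anchor's own content. The possible overlap and the floor effects make a low r harder to interpret. They do not make it a clean measure of responsiveness.

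**Conclusion.** The point holds for one of the two responsiveness indices. The rule that "the higher the absolute value, the more responsive the outcome is to change across time in the MBRT arm" is not sound for correlations compared across domains against this anchor, because it can rank an equally responsive, equally reliable outcome lower for its content. Alcohol misuse and suicidal ideation are the clearest cases. For aggression, trauma symptoms and depression the degree of mismatch cannot be judged from the documents.

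The size is unknown. The simulated range, about 60% to 97% against 50% for no bias, follows from the assumed gap in anchor correlation: a small gap gives a bias close to nothing, a wide gap a large one. The direction holds whenever the match differs. The SMR and relative-efficiency rankings stand as planned.

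**What to change.** In section 9.6:

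1. Do not use the anchor correlation to rank outcomes across domains. Base cross-outcome ranking on the SMR and relative efficiency.
2. Use the anchor correlation as a comparison of responsiveness only among outcomes whose content matches the anchor: resilience, perceived stress where it is analyzed, and burnout if its match to the anchor's items is justified in writing.
3. For all other self-report outcomes, report the correlation as association with perceived change in stress, job performance and resilience.

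Optionally, for cohorts not yet assessed post-course, add one change item per outcome domain and correlate each outcome with its own item.

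Steps 1 to 3 change analysis wording only. The price is that outcomes outside the anchor's domains keep one responsiveness index instead of two, and few outcomes remain to compare on r. The optional items add about five lines at one visit. They may be missing for the first cohort, whose post-intervention visit section 3 places in Year 2, Month 8, against Year 3, Months 3 to 4 for the second.

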## **Sample Size and Population**

We will recruit 104 law enforcement officers (52 at Albuquerque, 26 at Portland, and 26 at Madison). Using a 2:1.5:1 randomization allocation ratio for MBRT, SME, and NIC conditions, respectively, across three sites, 47 participants will be randomized to MBRT; 35 to SME; and 22 to NIC. Participants will be stratified by gender to ensure equivalent gender representation across conditions.

All participants will be invited to participate in individual feedback interviews via phone after the post-course assessment.

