The target population for our study is LEOs working in urban settings in the United States. LEOs will be recruited from Portland Police Bureau (PPB), Albuquerque Police Bureau (APB), and Madison Police Department (MPD). PPB employs 966 full-time, active duty officers, serving approximately 603,106 citizens in the Greater Portland Metropolitan Area; women and racial/ethnic minorities represent 16% and 16%, respectively. APD employs 921 full-time, active duty officers, serving approximately 907,301 citizens in the Greater Albuquerque Metropolitan Area; women and racial/ethnic minorities represent 16% and 47%, respectively. MPD employs 486 full-time, active duty officers, serving approximately 258,054 citizens in the Greater Madison Metropolitan Area; women and racial/ethnic minorities represent 28% and 21%, respectively. We will make concerted efforts to recruit a target final sample comprising  $\geq 16\%$  women and  $\geq 16\%$  racial/ethnic minorities in Portland,  $\geq 16\%$  women and  $\geq 35\%$  racial/ethnic minorities in Albuquerque,  $\geq 25\%$  women and  $\geq 20\%$  racial/ethnic minorities in Madison.

We will recruit 104 participants. Using a 2:1.5:1 randomization allocation ratio for MBRT, SME, and NIC conditions, respectively, across the three study sites, 47 participants will be randomized to MBRT; 35 to SME; and 22 to NIC. Our sample size is based on feasibility trial recommendations suggesting 12-25 participants per arm to optimize estimation of group means and variability without oversampling in terms of diminishing returns in parameter estimation, and to provide reasonably precise information in terms of confidence intervals around retention rates.

If we do not get an adequate response from either of the two departments, we will expand recruitment to neighboring police departments in the Greater Portland Metro and/or Albuquerque Metro areas.

All data collection will happen remotely, either online or via home-based collection and mail (for dried blood spot samples).

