estimates (i.e., Cronbach's alpha), and intraclass correlations will be estimated and checked for discrepancies between sites. Identified discrepancies will be investigated to determine site-specific issues that would undermine assumptions of conceptual and structural equivalence of measurement.

Given the optimization aim of our study, our analyses will not adjust for intraclass correlations across study arms (and any heterogeneity in those correlations). Our study will allow us to obtain information about the magnitude of intraclass correlations and the degree to which they are heterogeneous across study arms, which we will use for our data analysis plan in a future fully-powered efficacy RCT.

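### Reliability across sites is judged by Cronbach's alpha alone, which mixes measurement error with how varied each site's officers are

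*Combined protocol and SAP*

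**What the plan says.** Section 1.1, Objective 4, lists among its benchmarks for site equivalence "equivalence in outcome measure response distributions, reliability estimates, and intraclass correlations".

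Section 9.6 (Quantitative) carries this out: "Using baseline data (where sample size will be greatest) and pooling arms", the plan says that "distributions of standardized responses on outcome measures will be summarized, graphed, and compared across sites". It then says that unnamed key parameters are examined, and that reliability "estimates (i.e., Cronbach's alpha), and intraclass correlations will be estimated and checked for discrepancies between sites". On what follows, it says: "Identified discrepancies will be investigated to determine site-specific issues that would undermine assumptions of conceptual and structural equivalence of measurement".

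The documents do not define the standardization or the key parameters. They plan no site-level error variance or SEM, and they set no size of difference that counts as a discrepancy.

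**The concern.** Alpha is a ratio: roughly the share of total score variance that is not error. Site equivalence of measurement concerns the error part, meaning whether an officer at one site is measured as precisely as an officer at another. Alpha also moves with how much officers at a site truly differ from one another.

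The check can therefore mislead in two directions. A narrower officer mix lowers alpha although measurement is unchanged, and staff look for a procedural fault that is not there. Larger error combined with larger spread leaves alpha where it was, and the site counts as equivalent. The second direction is the less protected, because Section 9.6 investigates only discrepancies that have been identified.

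At stake is one part of the site-equivalence conclusion, which this trial is meant to supply for a later multisite efficacy trial.

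**Working it through.** The plan states no alpha, site SD or threshold for this comparison, so there is no figure of its own to reproduce.

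**Inputs from the documents.** Site sizes come from the Précis: "We will recruit 104 law enforcement officers (52 at Albuquerque, 26 at Portland, and 26 at Madison"; 52 + 26 + 26 = 104. Officer mix comes from Section 3. For Albuquerque, "women and racial/ethnic minorities represent 16% and 47%, respectively". For Madison, "women and racial/ethnic minorities represent 28% and 21%, respectively". Portland has 16% and 16%.

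**Assumptions.** A 10-item scale, parallel items, normal scores, constant error, and alpha 0.85 at the reference site. The SD ratios below are also assumed.

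**Formulas.** With true-score variance T and error variance of the scale mean E:
- alpha = T/(T + E)
- SEM = observed SD x sqrt(1 - alpha) = sqrt(E)

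At the reference site T = 1, so E = 0.15/0.85 = 0.176 and SEM = sqrt(0.176) = 0.42.

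**Same error, narrower spread.**
- True-score SD 25% smaller: T = 0.75² = 0.5625; alpha = 0.5625/(0.5625 + 0.176) = 0.76; SEM 0.42.
- True-score SD 40% smaller: T = 0.36; alpha = 0.36/(0.36 + 0.176) = 0.67; SEM 0.42.

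**Larger error, proportionally larger spread.**
- Both variances doubled: alpha = 2/(2 + 0.353) = 0.85; SEM = sqrt(0.353) = 0.59, and 0.59/0.42 = 1.41, so 41% larger.

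**Other reference values, error unchanged, true-score SD 0.8 times the reference.** Alpha 0.70 becomes 0.60, 0.80 becomes 0.72, and 0.90 becomes 0.85.

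**Does this show at 26 officers per site?** Two sites of 26 were simulated under the same assumptions, with 20,000 replicates.

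| Second site compared with the first | Alphas differ by at least 0.10 | SEM ratio (95% range) |
|---|---|---|
| Identical | 16% | 1.00 (0.88 to 1.14) |
| Same error, true SD 25% smaller | 46% | 1.00 (0.88 to 1.14) |
| Both variances doubled | about 16% | 1.41 (1.24 to 1.61) |

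By the alpha comparison, the third row cannot be told apart from identical sites. The SEM ratio separates them. SEM is estimated more tightly because it draws on (26 - 1) x (10 - 1) = 225 degrees of freedom, against 25 for the spread between officers.

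**Does SEM have a weakness of its own?** Yes. With ten items scored 0 to 4, an identical measurement process and only the site mean moved towards the floor, alpha went from 0.83 to 0.79 and SEM from 0.35 to 0.26, a fall of 0.09/0.35 = 26%. With only the spread changed, SEM on floor-limited items was nearly flat (0.300 against 0.303). SEM is thus robust to spread but not to score level.

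**The case against.** **Alpha is not the only site check.** Distributions, key parameters and intraclass correlations are compared too, and estimating variability is a stated aim of the trial, so site SDs may well be produced. This stands in part: an investigator following up a low alpha could find that spread explains it. But the key parameters are undefined. If responses are standardized within site, the spread needed to interpret alpha is removed. Intraclass correlations computed between persons share alpha's dependence on spread. Equal alphas also prompt no follow-up.

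**Unequal spread is not shown.** This stands. Section 3 gives gender and ethnic proportions, not score variances, and the same eligibility rules apply at every site. The mix makes unequal spread plausible and no more. Error and spread rising in exact proportion is a limiting case.

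**SEM should not simply replace alpha.** This stands. Officers in the severe range on depression, suicidal ideation, alcohol or PTSD screens are excluded (Section 4.2), so floor effects are plausible. Judged on SEM alone, a difference in site mean could then look like a difference in measurement.

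**Stronger readings a reader might infer.** One is that a single officer difference is scored as two failures, once on distributions and once on alpha. The documents have no failure count and no pass/fail threshold; discrepancies lead to an inquiry. Another is that single blood markers, which have no items and so no alpha, could be compared by their within-arm correlation from baseline to post-intervention. That correlation depends on spread just as alpha does, mixes in real change, and rests on few officers: 26 split 2:1.5:1 is about 12, 9 and 6 per arm, before the 20% attrition that Section 9.2 predicts.

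**Conclusion.** The concern holds as a minor point. Under the plan as written, agreement or disagreement of site alphas is not by itself evidence about measurement error, and the plan commits to nothing else that would separate error from spread.

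The algebra is exact for parallel items with constant, uncorrelated error. The sizes (0.85 to 0.76 with SEM unchanged; 0.85 retained with SEM 41% larger) rest on assumed SD ratios, item count and reference alpha. The claim is that alpha can mislead here; nothing in the documents shows that it will.

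Imprecision at 26 officers is a separate matter: identical sites differ by 0.10 or more in about 16% of samples under these assumptions. No arm comparison, measure ranking or sample size depends on this check.

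**What to change.** In Section 9.6, and by reference in Objective 4(b):

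- For each multi-item self-report scale, report by site at baseline the raw mean and SD (not standardized within site), alpha, and SEM = SD x sqrt(1 - alpha) with a bootstrap interval.
- Base the reliability part of the site-equivalence judgement on alpha and SEM, read together with the site mean and SD.
- State how the patterns are read. A lower alpha with a similar SEM and a smaller SD is an officer-mix difference. A larger SEM at a similar mean is investigated even when the alphas agree.
- State that SEM varies with score level on floor-limited scales, so an SEM difference that comes with a difference in site means is not by itself evidence of unequal measurement.

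The cost is a short change of wording and a few computed columns from baseline data already planned. The downside is that a reader must weigh four figures per scale and site instead of one.
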